# **8.2.1.1** Efficacy Endpoints

The descriptions of the efficacy measurements and time points at which they are measured are described in Section 4.2.3.1 and Section 6.0 (Trial Flow Chart), respectively. The efficacy endpoints to be analyzed are listed in Table 10. These endpoints will be analyzed at Week 52 as well as at Week 104 where applicable. Week 52 is the primary time point for efficacy analyses. Hypoglycemia is considered a safety endpoint.

In describing the efficacy variables of interest below, the description is restricted to the principal time points of interest (Week 52 and Week 104). However, many variables will be measured at additional time points, as indicated in the Trial Flow Chart (Section 6.0), and may be summarized at other time points.

Table 10 Efficacy Endpoints

Primary Endpoint				
Change from Baseline in A1C				
Key Secondary Endpoints				
Change from Baseline in				
Body weight				
Systolic blood pressure				
Other Endpoints				
Change from Baseline in				
FPG				
Proinsulin				
C-peptide				
Proinsulin/C-peptide ratio				
Homeostatic Model Assessment of β-cell function (HOMA-%β)				
Diastolic blood pressure				
Proportion of subjects with an A1C <7.0% and <6.5%				
Coefficient of durability (defined in Section 8.2.3.1)				
Proportion of subjects with an A1C decrease >0.5% with no symptomatic				
hypoglycemia and no body weight gain				
Proportion of subjects with an A1C $< 7.0\%$ with no symptomatic hypoglycemia				
Time to rescue				
Proportion of subjects requiring rescue medication				

#### 8.2.1.2 Safety Endpoints

The descriptions of the safety measurements and time points at which they are measured are provided in Section 4.2.3.2 and Section 6.0 (Trial Flow Chart), respectively. Tier 1 safety endpoints are listed in Table 13.

Part of the assessment of laboratory safety will be accomplished by defining limits of change for particular tests such that occurrences of subject values beyond these bounds are considered abnormal. Limits of change criteria are provided in Section 12.8. These criteria are based upon the laboratory normal ranges and abnormalities considered to be potentially clinically meaningful.

04T4BY Confidential

**Protocol/Amendment No.:** 002-01

# 8.2.1.3 Derivation of Efficacy Endpoints

The Homeostasis Model Assessment (HOMA) estimates steady state beta cell function ( $\%\beta$ ) as a percentage of a normal reference population. This endpoint will be derived using the updated HOMA model [18]. Fasting glucose and C-peptide will be used to calculate beta cell function ( $\%\beta$ ) using the calculator released from The University of Oxford in 2004 [19].

The Coefficient of Durability is described in Section 8.2.3.1.

Continuous endpoints that are a composite of more than one individual continuous endpoint (such as HOMA  $\%\beta$  and the ratio of proinsulin to C-peptide) must be computed based on samples collected on the same day.

# 8.2.2 Analysis Populations

Summaries of subject disposition will include all randomized subjects. Summaries of baseline characteristics will be performed in the All Subjects Treated (AST) population, consisting of all randomized and treated subjects.

# **8.2.2.1** Efficacy Analysis Populations

The FAS population will be the primary analysis population for all efficacy endpoints.

For analyses that use the cLDA model described in Section 8.2.3.1, the FAS population, defined separately for each analysis endpoint, consists of all randomized subjects who:

- receive at least one dose of study treatment;
- have a baseline measurement or a post-randomization measurement for the analysis endpoint subsequent to at least one dose of study treatment.

For secondary analyses that use the ANCOVA model with last-observation-carried-forward, the FAS population consists of all randomized subjects who took at least one dose of study treatment, and have measurements for the analysis endpoint both at baseline and at one or more post-baseline time points.

A secondary population for analyzing primary and key secondary efficacy endpoints at Week 52 and Week 104 will be the Per-Protocol (PP) population. All randomized subjects who take at least one dose of study medication, with a measurement of the analysis endpoint at both baseline and in the day range for the time point of interest (Week 52 or Week 104), without any of the following protocol deviations will be included in this population.

Protocol/Amendment No.: 002-01

• Drug compliance <75%, using the compliance definition provided in Section 8.2.9.

- Use of prohibited antihyperglycemic medications (found in Section 5.5) for a total of ≥14 days or ≥7 consecutive days after randomization and within 180 days prior to the analysis time point.
- Use of pharmacologic doses of corticosteroids for ≥2 consecutive weeks after randomization and within 180 days prior to the analysis time point
- Incorrect double-blind study medication, or a change in metformin dose, for  $\ge 14$  consecutive days during the last 180 days of the trial period of interest

Protocol deviations are not just a repetition of the exclusion and inclusion criteria in the protocol, but a clinical assessment of deviations from the protocol-specified criteria that will either affect or confound the measures of efficacy. Any patient meeting any of the above criteria during the trial period of interest (Week 0 to Week 52 or Week 0 to Week 104) will be excluded from the per-protocol population for that period.

The final determination on protocol deviations, and thereby the composition of the PP population, will be made prior to the final unblinding of the database at Week 52 and Week 104 and will be documented in separate memos.

A modified FAS (mFAS) population, defined as all subjects in the FAS who do not have any of the protocol deviations defined above, will be an additional secondary population. Subjects who discontinue prematurely without a protocol deviation will be included in the mFAS. Analyses will be performed in this population only if its size differs from that of the PP population by more than 2% of patients in any arm.

Any substantial differences between conclusions based on the FAS, PP, and (if applicable) mFAS populations will be investigated. The number of subjects included in the FAS, PP, and mFAS populations may vary across endpoints due to the degree of missing data for each endpoint.

Data after the initiation of rescue therapy or after a subject undergoes bariatric surgery will be censored (i.e., treated as missing) from analyses of efficacy endpoints.

The time-to-rescue analysis will be performed in the All-Subjects-Treated population.

For all efficacy analyses, subjects will be counted in the treatment group to which they were randomized, regardless of the treatment received during the course of the trial. Details on the approach to handling missing data are provided in Section 8.2.3, Statistical Methods.

**Protocol/Amendment No.:** 002-01

# 8.2.2.2 Safety Analysis Populations

The ASaT population will be used for the analysis of safety data in this trial. The ASaT population consists of all randomized subjects who took at least one dose of trial treatment. Subjects will be included in the treatment group corresponding to the trial treatment they actually took for the analysis of safety data using the ASaT population. This will be the treatment group to which they were randomized, except for any subjects who took incorrect trial treatment for the entire analysis period (Phase A or Phase A + Phase B). Such subjects will be included in the treatment group corresponding to the trial treatment actually received.

For lipid panel, laboratory, ECG and vital sign data, at least one measurement obtained subsequent to at least one dose of trial treatment is required for inclusion in the analysis of each specific parameter. To assess change from baseline, a baseline measurement is also required.

Safety analysis will be based on observed data only. No imputation will be performed for missing data except where noted otherwise.

#### 8.2.3 Statistical Methods

Statistical testing and inference for safety analyses are described in Section 8.2.3.2. Efficacy results that will be considered to be statistically significant after consideration of the strategy for controlling the Type I error are described in Section 8.2.5, Multiplicity. Nominal p-values may be computed for other efficacy analyses as a measure of strength of association between the endpoint and the treatment effect rather than formal tests of hypotheses. All statistical tests will be conducted at the  $\alpha$ =0.05 (2-sided) level. The primary objective on A1C is based on non-inferiority testing where the confidence interval rather than the p-value will be used to assess the primary hypothesis.

Analyses will be performed for Phase A alone and for Phase A + Phase B. Between-group comparisons for all efficacy and safety endpoints will be performed for both periods. The following comparisons will be made:

- ertugliflozin 15 mg vs. glimepiride
- ertugliflozin 5 mg vs. glimepiride

The results of adjudicated cardiovascular endpoints will not be presented in the clinical study report for this study. Analyses of these endpoints will be performed in the context of an integrated cardiovascular safety analysis involving the entire Phase II/III program. Details of these analyses will be provided in a separate statistical analysis plan.

**Protocol/Amendment No.:** 002-01

# **8.2.3.1** Statistical Methods for Efficacy Analyses

# Phase A (Week 0 to Week 52)

The primary efficacy analyses will compare the efficacy of ertugliflozin relative to glimepiride in change from baseline in A1C at Week 52. The mean change from baseline in A1C at Week 52 in the ertugliflozin 15 mg group will be compared to that in the glimepiride group using the estimated treatment difference via a constrained longitudinal data analysis (cLDA) model, proposed by Liang and Zeger [15]. This cLDA model assumes a common mean across treatment groups at baseline and a different mean for each treatment at each of the post-baseline time points. In this model, the response vector consists of baseline values and the values observed at each post-baseline time point. The cLDA model will include terms for treatment, time, prior antihyperglycemic medication (monotherapy or dual therapy), baseline eGFR, and the interaction of time by treatment. Time will be treated as a categorical variable so that no restriction is imposed on the trajectory of the means over time. The treatment difference in terms of mean change from baseline to a given time point will be estimated and tested from this model. Ertugliflozin 15 mg will be declared non-inferior to glimepiride in terms of A1C reduction if the upper limit of the two-sided 95% confidence interval (CI) for the mean difference between ertugliflozin 15 mg and glimepiride at Week 52 is less than the non-inferiority margin,  $\delta$ =0.3%. This margin was chosen because changes from baseline smaller than -0.3% have limited clinical impact, and the 0.3% margin balances lesser clinical impact with a study sample size that is feasible to conduct. The non-inferiority test for ertugliflozin 5 mg in A1C reduction will use the same approach described above following the multiplicity control strategy in Section 8.2.5. If non-inferiority is declared for ertugliflozin 15 mg, then an assessment of superiority will be conducted following the multiplicity control strategy described in Section 8.2.5. For the cLDA model, the Kenward-Roger adjustment will be used with restricted (or residual) maximum likelihood (REML) to make proper statistical inference. An unstructured covariance matrix will be used to model the correlation among repeated measurements and hence avoids the potential bias that could result from the use of specific structured covariance models. If the unstructured covariance model fails to converge with the default Newton-Raphson algorithm, the Fisher scoring algorithm or other appropriate methods can be used to provide initial values of the covariance parameters. In the rare event that none of the above methods yield convergence, a structured covariance such as Toeplitz can be used to model the correlation among repeated measurements. In this case, the empirical option will be used because the sandwich variance estimator is asymptotically unbiased while the model-based variance estimator can substantially overestimate or underestimate the true variance. The cLDA model uses the maximum likelihood principle to estimate the parameters and account for missing data in an implicit fashion. Values of eGFR that are >120 mL/min/1.73 m^2 will be set to 120  $mL/min/1.73 m^2$ .

**Protocol/Amendment No.:** 002-01

Although the baseline measurement is included in the response vector, it is independent of treatment, and hence, the baseline means are constrained to be the same for different treatment groups. Of note, in the event that there are no missing data, the estimated treatment difference from the above cLDA model will be identical to that from a traditional longitudinal analysis of covariance (ANCOVA) model which uses the baseline value as a covariate. However, unlike longitudinal ANCOVA, the cLDA model accounts for variability in the baseline values, thus providing more accurate standard errors and CIs for individual treatment effects. Moreover, this model allows the inclusion of subjects who are missing either the baseline or post-baseline measurements, thereby increasing efficiency. An example of SAS implementation code is given in Section 12.8.

All other continuous efficacy endpoints will be analyzed using the above cLDA method described for A1C

An analysis of covariance (ANCOVA) model will be used in the PP population as sensitivity analyses for the primary and key secondary efficacy endpoints at Week 52. The ANCOVA model will include treatment, prior antihyperglycemic medication, baseline eGFR, and baseline value. By definition, there will be no missing outcome data in the PP population.

The ANCOVA model as described above will also be used in the FAS population for the primary and key secondary efficacy endpoints. The last-observation-carried-forward (LOCF) method will be used to impute missing data.

If the size of the mFAS population (described in Section 8.2.2.1) differs from the size of the FAS by >2% in any treatment group, primary and key secondary endpoints will be analyzed in the mFAS population using the same cLDA methodology described for the FAS.

All continuous efficacy endpoints will be summarized and plotted over time by treatment group.

For the analysis of percentages of subjects at the A1C goals of <7.0% and <6.5% at Week 52, the constrained longitudinal data analysis (cLDA) model that is used for the analysis of A1C will be used to impute the missing data for A1C. Imputations of the missing data will be based on the marginal univariate normal distributions with means equal to the predicted values and variances equal to the squared standard errors for the predicted values from the cLDA model. Ten sets of imputations of each missing value will be constructed from the cLDA model. The seed for the random number generator will be 8835002. Observed data will not be imputed. Subjects will be categorized as at or not at the A1C goals (<7.0% or <6.5%) at Week 52 after imputation. An additional analysis of the percentages of subjects at A1C goals will treat all subjects with missing Week 52 data as not being at goal, regardless of the final observed A1C value.

To estimate the odds ratio, each of the 10 imputed data sets will be analyzed by logistic regression. The logistic regression model will include terms for treatment and baseline A1C. Parameter estimates on log odds ratio will be combined using standard multiple imputation techniques proposed by Rubin [20] to yield an overall estimate of log odds ratio. Log odds ratio will be back transformed into odds ratio for final reporting.

**Protocol/Amendment No.:** 002-01

A time-to-rescue analysis will also be performed. The proportion of subjects rescued in each treatment group will be summarized. Plots of the Kaplan-Meier estimate of the distribution of the time-to-rescue will be provided for each treatment arm and log-rank tests comparing the time-to-rescue distribution of ertugliflozin at a specific dose level versus glimepiride will be conducted. In this analysis, subjects will be censored at the time of discontinuation.

To assess the overall benefit of the trial treatment, the proportion of subjects meeting the composite endpoint of an A1C decrease >0.5% with no AE of symptomatic hypoglycemia and no weight gain by the end of Week 52 will be analyzed using the M&N method in the FAS population for both A1C and body weight at Week 52 [16]. Additionally, the proportion of subjects with an A1C < 7% with no symptomatic hypoglycemia at Week 52 will be analyzed using the same MN method in the FAS population for A1C. For both composite endpoints, missing data will be imputed via the LOCF method.

Durability of the ertugliflozin treatment effect will be evaluated by examining the time profile plot of mean change from baseline in A1C from Week 26 to Week 52, and from Week 26 to Week 104 for each group. In addition, the coefficient of durability (COD), defined as the slope of the time profile of mean change from baseline, will be derived via least squares from the cLDA model, using analysis time points beginning with Week 26. The estimation of COD provides a quantitative assessment for the rate of deterioration of a treatment after reaching its peak efficacy. A treatment with larger COD tends to be less "durable" than a treatment with smaller COD. The COD and its 95% CI will be provided. Standard errors for the COD will be computed by bootstrapping subjects within treatment groups.

A summary of the number (%) of subjects who initiate or have a change in anti-hypertensive medication (new medication or new dose) will be provided. Based on this summary, additional analyses of the blood pressure endpoints that censor data after initiation or changes in anti-hypertensive medication may be performed.

**Protocol/Amendment No.:** 002-01

Table 11 summarizes the analysis strategy for all efficacy endpoints. The strategy to address multiplicity issues is described in Section 8.2.5, Multiplicity.

Table 11 Analysis Strategy for Efficacy Endpoints

Endpoint/Variable (at Week 52 unless specified otherwise)	Approach	Statistical Method	Analysis Population	Missing Data Approach
Primary			- 0 0 0 0 0 0 0 0 0 0 0 0 0 0 0 0 0 0 0	
	P	cLDA	FAS	Model-based
	S	ANCOVA	PP	N/A
Change from baseline in A1C	S	ANCOVA	FAS	LOCF
	S	cLDA	m $FAS^{\dagger}$	Model-based
Key Secondary	•	•		
	P	cLDA	FAS	Model-based
Change from heading in he down ight	S	ANCOVA	PP	N/A
Change from baseline in body weight	S	ANCOVA	FAS	LOCF
	S	cLDA	m $FAS^{\dagger}$	Model-based
	P	cLDA	FAS	Model-based
Change from baseline in systolic blood	S	ANCOVA	PP	N/A
pressure	S	ANCOVA	FAS	LOCF
	S	cLDA	${ m mFAS}^{\dagger}$	Model-based
Other Endpoints				
Change from baseline in  FPG  C-peptide  Proinsulin  Proinsulin/C-peptide ratio  HOMA-%β  Diastolic blood pressure	Р	cLDA	FAS	Model-based
Proportion of subjects with A1C at goal (<7.0%, <6.5%)	P S	Logistic Regression	FAS	Multiple Imputation Missing=Not at Goal
Coefficient of durability	P	cLDA & bootstrap	FAS	Model-based

 
Proportion of subjects with an A1C decrease >0.5% with no symptomatic hypoglycemia and no body weight gain at Week 52
 
Proportion of subjects with an A1C < 7% with no symptomatic hypoglycemia
 
	P	M&N	FAS	LOCF
Time to rescue  Proportion of subjects requiring rescue medication  P=Primary; S=Secondary; M&N=Miettinen and	P	Kaplan Meier Log-rank	AST	N/A

<sup>†Analysis will be performed only if the sizes of mFAS and FAS differ by >2% in any treatment arm.

Protocol/Amendment No.: 002-01

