6.0	Study Flow Chart	The text 'Oxford' removed from Contact IVRS at Discontinuation Visit.	Typographical error corrected.
7.1.1.8.8	Medication Compliance Monitoring	The text 'Blinded investigational product but will' removed.	Typographical error corrected.
7.1.2.4	Body Weight	The text 'approximately' added.	Text added to clarify that the accuracy checks of scales are required approximately monthly.
7.1.3	Laboratory Procedures/Assessments	The text 'C-peptide' added to lists of laboratory tests masked from Visit 4/Randomization to the end of the study.	C-peptide masking was added to central laboratory specification; protocol modified to match specifications.
7.1.3.1	Laboratory Evaluations (Hematology, Chemistry, Urinalysis and Others)	Specified that 'Routine' laboratory safety tests required at least a 10-hour fast.	Text added for clarity.

7.1.4.2	Blinding/Unblinding	Duplicate sentence 'IVRS/IWRS should be used for emergency unblinding in the event that this is required for subject safety.' removed.	Typographical error corrected.
7.3.4	Clinical Adjudication Committee	Venous thromboembolic events and hospitalized heart failure incorporated into the paragraph summarizing the rationale for adjudication of cardiovascular (CV) events.	The list of CV events for adjudication includes venous thromboembolic and hospitalized heart failure events; summary paragraph updated for consistency.
8.1.1	Efficacy Analysis	Added 'baseline eGFR' into the	The level of renal function may
8.2.3.1	Statistical Methods for Efficacy Analyses	analysis models.	impact efficacy because ertugliflozin has a renal-based mechanism.
8.2.7	Subgroup Analyses and Effect of Baseline Factors		meenamsm.
8.1.1	Efficacy Analysis	Removed sentence saying that superiority for A1C will be declared if the upper bound of the 95% confidence interval excludes 0.	Details regarding the evaluation of superiority for A1C have been moved to Sections 8.1.3, 8.2.3.1, and 8.2.5.

**Protocol/Amendment No.:** 002-01

8.1.3 and 8.2.5	Multiplicity	• Revised the multiplicity schema to require success in the test of A1C for the 5 mg dose before testing other endpoints for the 5 mg dose while controlling the type 1 error rate at < 0.05.	Requested by regulatory agencies.
		Added an evaluation of superiority for A1C	• Allow an evaluation of superiority that preserves the overall type 1 error.

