# 8.1.1 Efficacy Analysis

The primary and key secondary endpoints, primary analysis population, and primary analysis method that will be employed for the efficacy analyses are presented in Table 9. To address the primary hypothesis that ertugliflozin is non-inferior to glimepiride in A1C reduction at Week 52, the change from baseline in A1C at Week 52 will be analyzed using a constrained longitudinal data analysis (cLDA) method proposed by Liang and Zeger [15]. The cLDA model will include terms for treatment, time, prior antihyperglycemic medication (monotherapy or dual therapy), baseline eGFR, and the interaction of time by treatment with the restriction of a common baseline mean across treatment groups. An unstructured covariance matrix will be used to model the correlation among repeated measurements. The comparisons of interest will be ertugliflozin 15 mg vs. glimepiride, and ertugliflozin 5 mg vs. glimepiride. The primary hypothesis regarding the non-inferiority of ertugliflozin 15 mg versus glimepiride in decreasing A1C will be assessed using the estimated treatment difference from the cLDA model. If the upper bound of the two-sided 95% confidence interval (CI) for the mean difference between ertugliflozin 15 mg and glimepiride is less than the non-inferiority margin,  $\delta = 0.3\%$ , then ertugliflozin 15 mg will be declared non-inferior to glimepiride in terms of A1C reduction at Week 52. The non-inferiority test for ertugliflozin 5 mg in A1C reduction will use the same approach described above for ertugliflozin 15 mg dose level under the multiplicity control strategy described in Section 8.1.3.

Analyses of the change from baseline in body weight and in systolic blood pressure at Week 52 will be performed using the cLDA model as described above.

The primary analysis time point will be Week 52.

Data obtained after the initiation of rescue therapy or after a subject undergoes bariatric surgery will be censored (i.e., treated as missing) in the analyses of efficacy endpoints to avoid the confounding influences of rescue therapy and bariatric surgery. The primary analysis population for all efficacy analyses will be the Full Analysis Set (FAS), comprised of all subjects who receive at least one dose of study therapy and have at least one measurement of the endpoint of interest (either at baseline or post-randomization).

Table 9 Summary of Analysis Strategy for Key Efficacy Endpoints

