#### 8.2 Statistical Analysis Plan

This section outlines the statistical analysis strategy and procedures for the trial. If, after the trial has begun, but prior to any unblinding, changes are made to primary and/or key secondary objectives, or the statistical methods related to those objectives, then the protocol will be amended (consistent with ICH Guideline E-9). Changes to exploratory or other non-confirmatory analyses made after the protocol has been finalized, along with an explanation as to when and why they occurred, will be listed in the Clinical Study Report (CSR) for the trial. Post-hoc exploratory analyses will be clearly identified in the CSR. No separate Statistical Analysis Plan (SAP) will be issued for this trial.

The statistical analysis of the data obtained from this trial will be the responsibility of the designee of the Sponsor.

This trial will be conducted as a double-blind trial. After all subjects complete Phase A (Visit 9/Week 52), medical/scientific review has been performed based on Phase A data, protocol deviators based on Phase A have been identified, and Phase A data have been declared final and complete, the trial will be unblinded to the Sponsor or the designee of the Sponsor. A CSR will be generated to support regulatory filing. This report will address the study's primary hypotheses and, hence, is not considered an interim analysis.

After Visit 9/Week 52, investigators and subjects will remain blinded to study drug treatment assignment until all subjects have completed the trial. At the end of the trial (including the 14 days after the last dose of blinded investigational product), the official, final database will be frozen and unblinded after medical/scientific review has been performed, protocol deviators have been identified, and data have been declared final and complete. A separate study report will be prepared after all subjects complete the trial.

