# Week 0 to Week 104 Analyses

All endpoints in Table 11 that are collected at Week 104 will also be analyzed at Week 104. Between-group comparisons will be provided for Week 104. Statistical models and analysis populations for Week 104 will be analogous to those at Week 52.

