# 8.2.6 Sample Size and Power Calculations

This trial will randomize approximately 1230 subjects into three treatment groups in a 1:1:1 ratio. A sample size of 410 per arm will be equivalent to an effective sample size of 337 per arm at Week 52 in the power calculation for the primary hypothesis test using the cLDA model in the FAS population. The effective sample size accounts for information loss due to missing data and the correlation among repeated measures, and is derived using the method proposed by Lu, et al. [21] under the assumptions of cumulative attrition rates and covariance matrix at Weeks 6, 12, 18, 26, 39 and 52 specified below. An effective sample size 337 per arm will provide 97% power to declare non-inferiority for a margin=0.3% in A1C reduction at Week 52 assuming the true mean difference in A1C between a given ertugliflozin dose level and glimepiride is 0% ( $\alpha$ =0.05, two-sided test) and the conditional standard deviation is 1.0% (Table 14).

The half-width of the 95% CI is expected to be 0.15%. The power for achieving success for both ertugliflozin doses will be approximately 95%. In the per-protocol population, the expected sample size is approximately 63% of the randomized population (257 subjects per arm).

Table 14 Power to Declare Non-inferiority in A1C at Week 52

		Power		95% CI
Population	N per Arm	Per Comparison	Both Comparisons	Half-width
FAS	337 †	97%	95%	0.15%
PP	257	92%	85%	0.17%

†Effective sample size, accounting for missing data and within-subject correlation of A1C over time. Based on a non-inferiority margin ( $\delta$ ) = 0.3%, true difference = 0%, standard deviation = 1%, and  $\alpha$  = 0.05 (2-sided).

Assumptions for the cumulative attrition rates and correlation matrix at Week 6, 12, 18, 26, 39 and 52 are listed below:

- Cumulative attrition rates at Weeks 6, 12, 18, 26, 39 and 52 are 0.073, 0.091, 0.112, 0.160, 0.210, and 0.312, respectively
- Conditional correlation matrix at Weeks 6, 12, 18, 26, 39 and 52 is

1	0.83	0.71	0.67	0.57	0.57
0.83	1	0.89	0.80	0.68	0.66
0.71	0.89	1	0.90	0.76	0.73
0.67	0.80	0.90	1	0.81	0.77
0.57	0.68	0.76	0.81	1	0.85
0.57	0.66	0.73	0.77	0.85	1

The above assumptions are derived based on data from MK-0431 P024.

Table 15 provides the detectable difference at 90% power for endpoints in the secondary hypotheses in the FAS population.

Protocol/Amendment No.: 002-01

Table 15 Power Calculations for Key Secondary Endpoints in the FAS Population

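### As listed, the primary cLDA gives prior therapy and baseline eGFR one coefficient each across baseline and all visits, so some of their precision gain can be lost and the claimed identity with ANCOVA fails

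*Combined protocol and SAP*

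**What the plan says.** Sections 8.1.1 and 8.2.3.1 define the primary analysis of A1C at Week 52 as a constrained longitudinal model. Baseline A1C is one of the responses, "with the restriction of a common baseline mean across treatment groups". Besides treatment and time, the listed terms are "prior antihyperglycemic medication (monotherapy or dual therapy), baseline eGFR, and the interaction of time by treatment". No covariate-by-time term appears.

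Section 8.2.3.1 makes a further claim for the case where every subject is fully observed: "the estimated treatment difference from the above cLDA model will be identical to that from a traditional longitudinal analysis of covariance (ANCOVA) model". The ANCOVA it has in mind adjusts for baseline. It then extends the model: "All other continuous efficacy endpoints will be analyzed using the above cLDA method". Under Week 0 to Week 104 Analyses the plan says: "Statistical models and analysis populations for Week 104 will be analogous to those at Week 52".

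Baseline eGFR was added by this amendment. The Summary of Changes gives as the reason that renal function may "impact efficacy because ertugliflozin has a renal-based mechanism".

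Two other places might have settled how the covariates enter, but do not. The sample code in Section 12.8 has no covariates and is offered only as an example. Section 8.2.7 does call for time-specific versions of its terms, but for a different model, the subgroup RMANCOVA.

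**The concern.** When baseline is a response, a covariate entered as a plain main effect is assumed to shift baseline A1C and Week 52 A1C by the same amount. A covariate that influences the response to treatment, rather than the starting level, does not behave that way. The model then compromises on one coefficient and recovers only part of the variance that the covariate could explain. The stated reason for adding eGFR concerns efficacy, which points to an effect on change, although no size is given. The documents do not say how prior therapy acts.

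Three things are at stake:

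- Some precision in the primary A1C estimate, and in every other endpoint that uses the same model.
- A statement of equivalence that the plan's own model does not satisfy.
- An ambiguity in the primary model. Two statisticians could read the list differently and report slightly different primary estimates, and no separate SAP will be issued to resolve it.

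**Working it through.** **Inputs from Section 8.2.6.** 410 subjects per arm; margin 0.3%; true difference 0; two-sided alpha 0.05; "the conditional standard deviation is 1.0" (% A1C); the 6 × 6 correlation matrix; cumulative attrition 0.073, 0.091, 0.112, 0.160, 0.210 and 0.312. The proportions last seen at baseline, Weeks 6, 12, 18, 26 and 39, and completing Week 52, are therefore 0.073, 0.018, 0.021, 0.048, 0.050, 0.102 and 0.688.

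**Assumed, because the documents give no values.** Baseline A1C SD 0.7; slope of later A1C on baseline 0.5; covariate effect on change of 0.1, 0.2 or 0.3% A1C per covariate SD.

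**Step 1: reproduce the plan.** Weighting the inverse covariance of each dropout pattern by its proportion, and inverting the sum, gives an effective size of 337.4 per arm (plan: 337). Then:

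- SE = √(2/337) = 0.0770
- half-width = 1.96 × 0.0770 = 0.151 (plan: 0.15)
- power = Φ(0.3/0.0770 − 1.96) = 97.4%; unrounded, 97.3% (plan: 97%)

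**Step 2: precision with three treatments of the covariate.** The plan's SD of 1.0 is taken to include covariate variation. Let v be the vector of covariate effects over the seven time points.

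- By-time model: residual covariance = total − vv′.
- Listed model: the common coefficient b is the generalised least squares compromise, solved iteratively, and the fitted covariance is that residual + (v − b1)(v − b1)′.

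For an effect on change only, b settles at 0.026, 0.053 and 0.085.

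| Effect on change | SE, no covariate | SE, as listed | SE, by time | SE loss as listed | Power, listed / by time |
|---|---|---|---|---|---|
| 0.1 | 0.07700 | 0.07691 | 0.07665 | 0.3% | 97.4 / 97.5% |
| 0.2 | 0.07700 | 0.07664 | 0.07560 | 1.4% | 97.5 / 97.8% |
| 0.3 | 0.07700 | 0.07614 | 0.07381 | 3.2% | 97.6 / 98.2% |

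For example, 0.07664/0.07560 − 1 = 1.4%. The listed model captures 24–27% of the available gain in these rows.

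**Step 3: vary the assumptions.**

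- Half the effect already present at baseline: loss 0.1, 0.3 and 0.7%.
- Equal effect at baseline and later, or no effect: loss 0.0%.
- Change-only effect, baseline SD 0.5–0.9 and slope 0.3–0.8: loss 0.2–4.2%, share of gain captured 2–58%, listed power 97.4–97.9%.
- If the SD of 1.0 is instead net of the covariates (baseline SD 0.6–0.9, same slopes, change-only effects of 0.2–0.3 per SD or a binary covariate with effect 0.3–0.5): listed residual variance is about 1–9% above by-time, and power is 96.2–97.3% against 97.3%.

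**Step 4: the identity.** In the listed model the covariate's coefficient given baseline is forced to be b × (1 − slope). In ANCOVA it is free. For a change-only effect of 0.2, the listed model implies about 0.053 × (1 − 0.5) = 0.027, where ANCOVA would estimate about 0.2. The two cannot be identical in general.

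In complete-data simulations (200 trials per setting), the listed estimate minus same-covariate ANCOVA had RMS 0.006, 0.012 and 0.018% A1C for the three change-only effects. It was 0.002 for no effect or for an equal effect of 0.2. A model without covariates, and one with covariates by time, each matched its own ANCOVA within 2 × 10⁻¹². Mean estimates of the listed and by-time models agreed within 0.001, so there is no material bias.

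Body weight and systolic blood pressure are not quantified, because the plan gives no correlations for them.

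**The case against.** The main case against is that this changes nothing of consequence. The listed model is valid, power moves by 0.1 to 0.6 points in the table above, and no decision rule uses the identity sentence, which is explanatory and applies only with complete data while the plan expects 31.2% attrition. All of that stands.

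A sharper point is that the renal rationale is specific to ertugliflozin, so it suggests a treatment-by-eGFR effect rather than one common to all arms. With the effect on change confined to the ertugliflozin arms, the true SE loss is 0.07, 0.26 and 0.59% for the three effect sizes, and the loss in the model-reported SE is 0.15, 0.62 and 1.41%. This stands too. It places the eGFR loss towards the low end of the range, and by-time terms alone would not model such an interaction. The larger losses also need a sizeable assumed effect: 0.3% per covariate SD equals the whole non-inferiority margin.

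It is also argued that the listed model is never worse than omitting the covariates. That is true of the scenarios in the table but not in general. With an effect of 0.2 at baseline and 0.1 later (baseline SD 0.6 or 0.9, slope 0.3–0.8), the residual variance relative to by-time terms is 1.004–1.010 as listed, against 1.000–1.003 with no covariate.

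Finally, Week 52 ANCOVA with the same covariates is already planned in the per-protocol population and with LOCF. It is a useful cross-check, but the populations and missing-data handling differ, so it does not stand in for the primary model.

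**Conclusion.** The concern holds. As listed, each covariate has a single coefficient across baseline and all later visits, and the exact equivalence with ANCOVA is false for that model whatever the true covariate effects. The precision loss is conditional and small: 0.0% if the covariates act equally at baseline and Week 52, and 0.2–4.2% of the SE over the assumed range if they act only on change. These sizes rest on assumed covariate effects, baseline SD and slope. The stated 97% power reproduces and is not threatened, and the non-inferiority conclusion is not at risk. The point is worth correcting because it concerns the primary model, the text admits two readings, and the better model costs almost nothing.

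**What to change.** In Sections 8.1.1 and 8.2.3.1, specify prior antihyperglycemic medication by time and baseline eGFR by time in the cLDA for A1C and the other continuous efficacy endpoints. If these terms are already intended, say so. Limit the identity sentence in 8.2.3.1 to longitudinal ANCOVA with the same covariates; with by-time terms it is then correct.

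This needs a protocol amendment before unblinding. Section 8.2 says that if changes are made to primary or key secondary objectives, "or the statistical methods related to those objectives, then the protocol will be amended". The text change is a few words. It adds 2 × 6 = 12 parameters to the Week 52 model and 2 × 10 = 20 to the Week 104 model, with about 1230 subjects and no extra data. When a covariate has no effect there is no SE cost (0.0697 under both models in complete-data simulation).
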